1.6 STATISTICAL MODIFICATIONS MADE IN THE STATISTICAL ANALYSIS PLAN

The statistical analysis plan history table below gives the timing, rationale, and key details for major changes to the statistical analysis features in the statistical analysis plan and/or protocol.

SAP version Number	Date Approved	Rational	Description of statistical changes
1	30-Apr-2020		Original SAP
2	05-May-2020	Change the interim analysis timing and clarify the scope of adaptations the Sponsor may make based on the interim analysis results according to Protocol Amendment 3	
 Remove requirement that the interim analysis requires data up to Day 15 in section 3 Interim analysis. Specify the type of modifications that the Sponsor may make based on the interim analysis results in section 3 Interim analysis.

2 STATISTICAL AND ANALYTICAL PROCEDURES

2.1 ANALYSIS ENDPOINTS

2.1.1 Demographic and baseline characteristics

In general, the baseline value is defined as the last available value prior to the first dose of investigational medicinal product (IMP) or the last available value on or before the date of randomization for patients who were randomized but never exposed to IMP, unless otherwise specified.

Demographic characteristics

The following demographic characteristics will be summarized separately by treatment and overall:

- Age at screening (years)
- Age group (≥ 18 and < 64 , ≥ 65 and < 84 , ≥ 85 years)
- Sex (Male, Female)
- Race (White, Black or African American, Asian, American Indian or Alaska Native, Native Hawaiian or Other Pacific Islander, Not Reported, Unknown). Note: Japanese will be included in Asian
- Ethnicity (Hispanic or Latino, Not Hispanic or Latino, Not Reported, Unknown)
- Baseline height (cm)
- Baseline weight (kg)
- Baseline weight category (< 50 , 50 to < 100 , ≥ 100 kg)
- Baseline body mass index (BMI, kg/m^2) (< 18.5 , 18.5 to < 25 , 25 to < 30 , ≥ 30)

Disease characteristics at baseline

The following baseline disease characteristics will be summarized:

- Severity of illness (per IRT) (Severe, Critical)
- Severity of illness (as recorded on CRFs) (Severe, Critical)
- Systemic corticosteroids use (per IRT) (Yes, No)
- Systemic corticosteroids use (as recorded on CRFs) (Yes, No)
- Clinical status using 7-point ordinal scale
- Body temperature prior to dosing ($^{\circ}\text{C}$) (defined as the highest temperature at any time prior to first dose)
- Fever (Yes, No)

- SARS-CoV-2 virus detected (Positive, Negative)
- CRP level

The other baseline disease characteristic includes

- Pneumonia status
 - Pneumonia present based on historical chest X-Ray, CT scan or MRI or lung auscultation (Yes, No)
 - Signs and symptoms: Fever, Cough, Dyspnea (Yes, No)
 - Time from dyspnea onset to baseline
 - Type of oxygen delivery device (Nasal cannula, simple face mask, non-rebreather face mask, high-flow nasal cannula, non-invasive ventilation, invasive mechanical ventilation, other)
 - Use of extracorporeal life support life support (Yes, No)
 - Use of renal replacement therapy (Yes, No)
 - Use of vasopressors (Yes, No)
- Oxygen administration and oxygenation
 - Supplemental Oxygen or mechanical ventilation used (Yes, No)
 - Oxygen flow rate (L/min)
 - Oxygen saturation (SpO₂ %) (range is 0% to 100%)
 - FiO₂ (fraction of inspired oxygen) (range is 0.0 to 1.0) – see [Section 2.5.2](#) for derivations
 - SpO₂/FiO₂ ratio – see [Section 2.5.2](#) for derivations
- Hospitalization and ICU admission
 - Duration of hospitalization prior to dosing
 - ICU required (Yes, No)
 - If yes, ICU admitted (Yes, No)
 - Duration of ICU admission prior to dosing

Medical history

Medical history, concomitant diseases or past surgeries or surgical history are recorded.

This information will be coded using the version of Medical Dictionary for Regulatory Activities (MedDRA) currently in effect at Sanofi at the time of database lock.

Any technical details related to computation, dates, and imputation for missing dates are described in [Section 2.5](#).

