#### Age

I 01. Participant must be  $\geq 18$  years of age inclusive, at the time of signing the informed consent.

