1 OVERVIEW AND INVESTIGATIONAL PLAN

1.1 STUDY DESIGN AND RANDOMIZATION

This study is a randomized, double-blind, placebo-controlled, phase 3 trial to evaluate the efficacy and safety of sarilumab in hospitalized adults with severe or critical COVID-19. The study will be conducted in Europe and other countries except in the United States (US) in up to 100 sites.

Approximately 400 patients will be randomized via interactive response technology (IRT) in a 2:2:1 allocation ratio to sarilumab 400 mg IV, sarilumab 200 mg IV, or placebo. Randomization will be stratified by severity of illness (severe, critical) and use of systemic corticosteroids (yes, no), and balanced by region. All patients will receive a single dose of study drug on Day 1. Patients may receive a second dose with study drug (based on the original treatment group assigned) 24 to 48 hours after the first dose, if they meet prespecified criteria in protocol.

Severity of illness categories:

- Severe disease:
 - Requires supplemental oxygen administration by nasal cannula, simple face mask, or other similar oxygen delivery device
- Critical disease:
 - Requires supplemental oxygen requiring delivered by non-rebreather mask or high flow nasal cannula, or
 - Use of invasive or non-invasive ventilation, or
 - Requiring treatment in an intensive care unit.

Patients will be assessed daily while hospitalized. Patients discharged from the hospital prior to Day 29 will be contacted with a follow-up phone call on Day 29 to assess status and occurrence of re-admission to a hospital. Patients will undergo a series of efficacy, safety and laboratory assessments while in the hospital. Serum IL-6 and other markers will be collected and analyzed in a central laboratory. Nasopharyngeal (NP) samples to monitor viral infection and blood samples may be obtained on Day 1 (pre-dose), 4, 7, 15, 29 (or up until the day of discharge if the patient is discharged from the hospital before Day 29). An individual patient will complete the study approximately 60 days from screening to follow-up on day 60 ± 7 days. Patients will not be required to return to the hospital once discharged.

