For patients who die, the clinical status recorded on the day of death will be replaced with “1=Death” and this value will be carried forward for all subsequent study days until end of study (Day 60). Death date may be obtained from Adverse Events or Disposition CRFs or phone call at Day 60 (end of study).

For patients who discharge early (other than death), the clinical status recorded on the earliest hospital discharge date will be replaced with 7 (not hospitalized), and this value will be carried forward for all subsequent study days until end of study (Day 60). Hospital discharge information (discharge date and discharge reason) may be obtained from the Discharge Reason eCRF. If there is subsequent hospitalization, the clinical status will not be replaced by 7 after the second hospitalization.

Handling of missing data on clinical status assessment (post-baseline)

For patients who are alive and not discharged (ie, still hospitalized), missing clinical status value (ordinal scale) on a given study day will be imputed using data on the type of oxygen delivery device used by the patient on that day (last type of device used if multiple types were used in a day).

Clinical status = 2 (if using invasive mechanical ventilation or ECMO), or
= 3 (if using non-invasive mechanical ventilation or high-flow nasal cannula), or
= 4 (if using nasal cannula, simple face mask, or non-rebreather face mask) or
= 5 (if not using supplemental oxygen)

Sensitivity analysis

The PPS and ITT will be used for sensitivity analysis of the primary efficacy endpoint, as described above.

Subgroup analyses

Descriptive analyses will be performed on the primary endpoint to summarize the treatment effect of each sarilumab dose versus placebo by the following variables:

- Age (<median, >=median)
- Age group (≥ 18 and < 64 , ≥ 65 and < 84 , ≥ 85 years)
- Sex (Male, Female)
- Race (White, Black or African American, Asian, Other). Note: Japanese will be grouped with Asian, a group with less than 5 patients in any treatment may be grouped with 'Other'
- Ethnicity (Hispanic or Latino, Not Hispanic or Latino)
- Severity of illness (per IRT) (Severe, Critical)
- Severity of illness (as recorded on CRFs) (Severe, Critical)
- Systemic corticosteroids use (per IRT) (Yes, No)
- Systemic corticosteroids use (as recorded on CRFs) (Yes, No)
- Fever status at baseline (Yes, No)
- Pneumonia present based on historical chest X-Ray, CT scan or MRI or lung auscultation (Yes, No)

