2.4.5 Analyses of safety data

The summary of safety results will be presented by treatment group.

General common rules

All safety analyses will be performed on the safety population as defined in [Section 2.3.2](#), unless otherwise specified, using the following common rules:

- The baseline value is defined as the last available value prior to the first dose of study medication.
- The potentially clinically significant abnormality (PCSA) values are defined as abnormal values considered medically important by the Sponsor according to predefined criteria/thresholds based on literature review and defined by the Sponsor for clinical laboratory tests, vital signs, and ECG (see [Appendix A](#))
- PCSA criteria will determine which patients had at least 1 PCSA during the treatment-emergent adverse event period, taking into account all evaluations performed during the treatment-emergent adverse event period, including nonscheduled or repeated evaluations. The number of all such patients will be the numerator for the on-treatment PCSA percentage.
- The treatment-emergent PCSA denominator by group for a given parameter will be based on the number of patients assessed for that given parameter in the treatment-emergent adverse event period by treatment group on the safety population.
- For quantitative safety parameters based on central laboratory/reading measurements, descriptive statistics will be used to summarize results and change from baseline values by visit and treatment group. Summaries will include the endpoint value. The endpoint value is commonly defined as the value collected at the same day/time of the last dose of investigational product. If this value is missing, this endpoint value will be the closest one prior to the last dose intake.
- Selected safety analyses will be summarized by age group, gender, racial subgroups, and any pertinent subgroups as appropriate (eg, number of doses administered).

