2.5 DATA HANDLING CONVENTIONS

2.5.1 General conventions

The following formulas will be used for computations of parameters.

Demographic formulas:

Age at baseline is calculated as follows:

$$\text{Age} = (\text{informed consent date} - \text{birth date})/365.25$$

BMI is calculated as follows:

$$\text{BMI} = \text{Weight in kg}/(\text{height}^2 \text{ in meters}).$$

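### The SAP's three-level age grouping assigns patients aged 64 and 84 to no group, so one demographic row and one of 17 descriptive subgroup variables are incomplete as written

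*SAP*

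**What the plan says.** - **Demographic list (SAP 2.1.1).** Age is summarised twice: as a continuous variable, "Age at screening (years", and in three categories, "Age group (≥ 18 and < 64 , ≥ 65 and < 84 , ≥ 85 years".
- **Primary-endpoint subgroups (SAP 2.4.4.1).** The same three categories appear again with the same limits. The line above them is a second age variable, "Age (<median, >=median". For every listed subgroup variable the section asks for hazard ratios against placebo, a treatment-by-subgroup interaction p-value and a forest plot. It labels these analyses descriptive.
- **Safety (SAP 2.4.5).** "Selected safety analyses will be summarized by age group, gender, racial subgroups, and any pertinent subgroups as appropriate". No age cut-points are given here.
- **How age is computed (SAP 2.5.1).** Age is the number of days from birth to informed consent, divided by 365.25. No truncation or rounding rule is stated.
- **Who is eligible (Protocol 5.1, I 01).** Entry requires at least 18 "years of age inclusive, at the time of signing the informed consent". There is no upper limit, so patients aged 64 and 84 can be enrolled.
- **Missing categories (SAP 2.5.3).** Unless stated otherwise, patients with a missing categorical value are left out of percentages. Counts of missing values are shown when relevant.

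**The concern.** The first category stops below 64 and the second starts at 65. The second stops below 84 and the third starts at 85. Each boundary therefore leaves a gap one year wide.

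A programmer who follows the text must either leave these patients unclassified or choose a repair that the SAP does not specify. Two repairs are natural: raise the upper limits to <65 and <85, or lower the next lower limits to ≥64 and ≥84. They put 64- and 84-year-olds in different groups and could give different age-group hazard ratios.

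If the patients are left unclassified and coded as missing, the rule in SAP 2.5.3 allows the age-group percentages to add to 100% on a reduced denominator. The omission would then be easier to overlook.

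**Working it through.** The plan states no figure on this point, so there is nothing to reproduce. The check has two parts: which ages are unassigned, and how many patients that might be.

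**1. Which ages fall in no group**

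The categories were coded literally as [18, 64), [65, 84) and [85, ∞). Every whole-year age from 18 to 110, and every age in steps of 0.01 year, was tested for membership.

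| Version of the limits | Whole-year ages unassigned | Decimal ages unassigned |
|---|---|---|
| As written: <64, <84 | 64 and 84 | 64.00 to 64.99 and 84.00 to 84.99 |
| With ≤64 and ≤84 | none | 198 grid values, between 64 and 65 and between 84 and 85 |
| With <65 and <85 | none | none |

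No age falls in two categories under the written limits.

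A rounding convention does not close the gap. A patient aged 64.7 is unassigned on the decimal scale. Truncated to 64, the patient is still neither below 64 nor at least 65.

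An error in reading the PDF is unlikely. The same limits appear in two separate lists, and ≤ signs survive elsewhere in the SAP, for example in the fever thresholds and the dyspnea-onset subgroup. Nor is it a house convention: the weight and BMI categories in the same demographic list are contiguous.

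**2. How many patients**

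Inputs:
- Planned total of about 400 (SAP 1.1: "Approximately 400 patients will be randomized via interactive response technology (IRT").
- Age distribution: not in the documents. Assumed normal with mean m and SD s, truncated at 18.

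Formula, with Φ the standard normal distribution function:

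P(unclassified) = { [Φ((65−m)/s) − Φ((64−m)/s)] + [Φ((85−m)/s) − Φ((84−m)/s)] } / [1 − Φ((18−m)/s)]

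| m | s | Aged 64 | Aged 84 | Total | × 400 |
|---|---|---|---|---|---|
| 50 | 12 | 1.61% | 0.05% | 1.66% | 6.6 |
| 55 | 14 | 2.27% | 0.31% | 2.58% | 10.3 |
| 60 | 14 | 2.71% | 0.62% | 3.33% | 13.3 |
| 65 | 12 | 3.32% | 0.89% | 4.21% | 16.8 |
| 70 | 12 | 2.99% | 1.60% | 4.59% | 18.4 |

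Over the full grid (m from 50 to 70, s of 12, 14 and 16) the total runs from 1.66% to 4.59%, or about 7 to 18 of 400. Most of these patients are aged 64.

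Each hazard ratio compares one dose with placebo. On the sizes in SAP 1.3 (about 160 and 80) that is 240 patients: 240 × 0.0166 ≈ 4 and 240 × 0.0459 ≈ 11. So about 4 to 11 patients would be absent from each age-group comparison.

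**3. Where these patients are and are not lost**

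- Demographic table: lost from the age-group row only. They stay in the mITT population, the continuous age row and every other row.
- Primary-endpoint subgroups: SAP 2.4.4.1 lists 17 variables. They are lost from one and stay in 16, including the median-age split.
- Safety by age: lost only if the same cut-points are applied. The three-level grouping is the only definition labelled age group in the SAP, so this is a reasonable inference, but it is not stated.
- Primary log-rank test, key secondary CMH test, testing hierarchy and overall safety tables: none uses age group, so none is affected.

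**The case against.** The strongest reply is that this is a drafting slip with an obvious intended meaning (under 65, 65 to 84, 85 and over). A row that does not add up to its column total would probably be noticed when tables are checked. No inferential result depends on it. The subgroup analyses are descriptive, the interaction p-value lies outside the multiplicity procedure, and a complete age subgroup analysis already exists in the median split. Exclusion depends on baseline age, not on treatment or outcome, so it does not by itself bias the comparison with placebo.

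Most of this stands, and it limits the point to minor severity. It does not remove the point. The meaning seems obvious, but the SAP does not state it. Detection from the row total is also less certain if unclassified patients are treated as missing and left out of percentages.

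A reader might infer that patients aged 64 and 84 drop out of the demographic table, the subgroup analysis and the safety-by-age tables altogether. The documents do not support that. These patients appear in every other demographic row and in 16 of the 17 subgroup variables, and SAP 2.4.5 covers only selected safety analyses, without cut-points.

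**Conclusion.** Wrong as written, and minor. The three-level age grouping omits ages 64 and 84 in both places where it is defined, and nothing else in the SAP closes the gap. The certain effect is confined to one demographic row and one descriptive subgroup variable. An effect on safety-by-age summaries is conditional on shared cut-points.

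The existence of the gap needs no assumption. Its size does: about 2% to 5% of patients, or 7 to 18 of 400, rests entirely on assumed normal age distributions. Nothing here shows a material change in any treatment estimate, and the primary, key secondary and overall safety conclusions stand as planned.

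**What to change.** In SAP 2.1.1 and in the subgroup list of SAP 2.4.4.1, change the age groups to ≥18 and <65, ≥65 and <85, and ≥85 years. These limits place every eligible age in exactly one group, whether age is kept as a decimal or truncated to whole years. Changing < to ≤ at 64 and 84 would be weaker, because it works only if age is first truncated.

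Add one sentence to SAP 2.4.5 saying that safety summaries by age use the same groups. It would also help to state in SAP 2.5.1 whether age is truncated for display and grouping.

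The main change is two numbers in each of two lists. It affects no hypothesis, significance level or sample size. It should be made before the primary database lock so that the limits are fixed in advance.

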2.1.2 Concomitant medications

All medications taken from screening to day 60 (or until day of discharge from hospital if before Day 60) captured include:

- Corticosteroids, NSAIDs, and any other anti-pyretics
- Antivirals (eg, remdesivir), antifungals, antibacterials, antimycobacterials, antiprotozoans, antihelminthics, antimalarials (eg, chloroquine and hydroxychloroquine)
- Interferon beta and convalescent serum.
- Angiotensin converting enzyme and Angiotensin receptor blocking
- Agents that may affect the CYP450 substrate.
- Any rescue medication that is used during the course of the study.

All medications will be coded using the World Health Organization – Drug Dictionary (WHO-DD) version currently in effect at Sanofi at the time of database lock.

Concomitant medications are any treatments received by the patient concomitantly to the IMP, during the treatment-emergent period (as defined in the observation period in [Section 2.1.4](#)).

During the study, for patients requiring rescue therapy as per the judgement of the study physician, additional medications may be utilized. Rescue medications are defined as the immunosuppressive therapies (described in the exclusion criteria E03 and E04).

Any technical details related to computation, dates, imputation for missing dates are described in [Section 2.5](#).

2.1.3 Efficacy endpoints

2.1.3.1 Primary efficacy endpoint(s)

The primary endpoint is the time to improvement of 2 points in clinical status assessment from baseline using the 7-point ordinal scale.

The 7-point ordinal scale is an assessment of the clinical status. The scale is as follows:

- 1. Death;
- 2. Hospitalized, on invasive mechanical ventilation or extracorporeal membrane oxygenation (ECMO);
- 3. Hospitalized, on non-invasive ventilation or high flow oxygen devices;
- 4. Hospitalized, requiring supplemental oxygen;
- 5. Hospitalized, not requiring supplemental oxygen - requiring ongoing medical care (COVID-19 related or otherwise);
- 6. Hospitalized, not requiring supplemental oxygen - no longer requires ongoing medical care

- 7. Not hospitalized

2.1.3.2 Secondary efficacy endpoint(s)

The key secondary endpoint is the proportion of patients alive at Day 29.

Other secondary endpoints are:

1. Proportion of patients with one-point improvement from baseline in clinical status assessment at days 4, 7, 15, 21, 29 using the 7-point ordinal scale
2. Mean change in 7-point ordinal scale from baseline to days 4, 7, 15, 21, 29 (or until discharge)
3. Time to resolution of fever defined as body temperature ($\leq 36.6^{\circ}\text{C}$ [axilla], or $\leq 37.2^{\circ}\text{C}$ [oral], or $\leq 37.8^{\circ}\text{C}$ [rectal or tympanic]) for at least 48 hours without antipyretics or until discharge, whichever is sooner
4. Time to resolution of fever (as defined above) and improvement in oxygenation (as defined below)
5. Days with fever ($>37.4^{\circ}\text{C}$ [axilla], or $>38.0^{\circ}\text{C}$ [oral], or $>38.4^{\circ}\text{C}$ [rectal or tympanic]) based on maximum value observed during a 24-hour period.
6. Time to change in National Early Warning Score 2 (NEWS2) from baseline
7. Time to NEWS2 of <2 and maintained for 24 hours
8. Mean change from baseline to Day 4, 7, 15, 21, 29 in NEWS2
9. Time to improvement in oxygenation (SpO₂/FiO₂ of 50 or greater) compared to the nadir for at least 48 hours, or until discharge, whichever is sooner
10. Alive off supplemental oxygen at Day 29
11. Days of hypoxemia (SpO₂ $<93\%$ on room air, or requiring supplemental oxygen, or mechanical ventilatory support)
12. Days of supplemental oxygen use
13. Days of resting respiratory rate >24 breaths/min (maximum value if recorded at more than once a day)
14. Time to saturation $\geq 94\%$ on room air
15. Ventilator free days in the first 28 days (to Day 29)
16. Initiation of mechanical ventilation, non-invasive ventilation, or use of high flow nasal cannula (for those not requiring these interventions at baseline)
17. Proportion of patients requiring rescue medications during the 28-day period
18. ICU status (among those not in an ICU at baseline, record if transferred to the ICU or the need to transfer to the ICU [if the ICU is not available])
19. Days of hospitalization among survivors

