#### Type of participant and disease characteristics

I 02. Hospitalized for less than or equal to 7 days (or documentation of a plan to admit to the hospital if the patient is in an emergency department) with illness of any duration with evidence of pneumonia by chest radiograph, chest computed tomography or chest auscultation (rales, crackles)

AND meets at least one of the following prior to randomization (patients meeting more than one criterion will be categorized in the most severely affected category).

Participants who are with a:

- Severe disease:

Requires supplemental oxygen administration by nasal cannula, simple face mask, or other similar oxygen delivery device (ie. increase in oxygen requirement following COVID infection).

- Critical disease:

- Requires supplemental oxygen delivered by non-rebreather mask or high-flow nasal cannula

OR

- Use of invasive or non-invasive ventilation

OR

- Requiring treatment in an intensive care unit.

I 03. Laboratory-confirmed SARS-CoV-2 infection (eg, by PCR), or other commercial or public health assay in any specimen within 2 weeks prior to randomization and no alternative explanation for current clinical condition.

I 04. Willing and/or able to comply with study-related procedures/assessments

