1.2.2 Secondary objectives

- Evaluate the 28-day survival rate
- Evaluate the clinical efficacy of sarilumab compared to the control arm by clinical severity
- Evaluate changes in the National Early Warning Score 2 (NEWS2)
- Evaluate the duration of predefined symptoms and signs (if applicable)
- Evaluate the duration of supplemental oxygen dependency (if applicable)
- Evaluate the incidence of new mechanical ventilation use during the study
- Evaluate the duration of new mechanical ventilation use during the Study
- Evaluate the proportion of patients requiring rescue medication during the 28-day period
- Evaluate need for admission into intensive care unit (ICU)
- Evaluate duration of hospitalization (days)
- The secondary safety objectives of the study are to evaluate the safety of sarilumab through hospitalization (up to Day 29 if patient is still hospitalized) compared to the control arm as assessed by incidence of:
 - Serious adverse events (SAEs)
 - Major or opportunistic bacterial or fungal infections in patients with grade 4 neutropenia
 - Grade ≥ 2 infusion related reactions
 - Grade ≥ 2 hypersensitivity reactions
 - Increase in alanine transaminase (ALT) $\geq 3X$ ULN (for patients with normal baseline) or $>3X$ ULN and at least 2-fold increase from baseline value (for patients with abnormal baseline)
 - Major or opportunistic bacterial or fungal infections

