The analysis for time to change in NEWS2 from baseline will be performed by evaluating the proportion of patients with clinical risk over time in each category (Low: 0-4; Low-medium: 3 in any individual parameter; Medium: 5-6; High: ≥ 7). The pattern of patients in the categories shifting from baseline and over time will be examined with no formal testing.

The time to NEWS2 < 2 and maintained for 24 hours endpoint will be analyzed similarly to the primary endpoint.

Patients who do not experience endpoint event under analysis will be censored at the last observation time point. Patients who die or take rescue medication in the study without experiencing the event will be censored at the earlier date of death or rescue medication started.

Analyses of endpoint #8: Mean change from baseline to Day 4, 7, 15, 21, 29 in NEWS2

Change from baseline in NEWS2 score at Day 4, 7, 15, 21, and 29 will be analyzed using an ANCOVA model with treatment group and randomization strata as fixed effects, and baseline value as a covariate. The least squares (LS) treatment mean difference from placebo with standard error, along with corresponding 95 % confidence interval and p-value will be provided. Graphical presentations (line plot with mean and error bar) will also be used to examine trends over time using mean values (\pm SE) and mean changes from baseline (\pm SE).

NEWS2 score at each day and their changes from baseline will be summarized for each treatment group through descriptive statistics including mean, median, standard deviation, minimum and maximum.

ICU use, rescue medication, hospitalization and other

Analyses of endpoint #17: % of patients requiring rescue medication during the 28-day period, #18: % of patients with ICU use (among those not in an ICU at baseline)

These endpoints will be analyzed using a CMH method stratified by randomization strata. The difference in proportions of patients for each Sarilumab dose compared to placebo (sarilumab - placebo), along with associated 2-sided 95% confidence levels, and p-value will be provided.

Bar plots will be provided to illustrate the difference among treatments. Summary of immunosuppressive medications used as rescue therapy over time will also be provided.

Analyses of endpoint #19: Days of hospitalization among survivors

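### Secondary endpoint #18 (ICU status) sets its denominator by where the patient is, not by need, so ICU need present before dosing can be counted as an outcome

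*SAP*

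**What the plan says.** Five places in the documents bear on the point.

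- **Definition (SAP 2.1.3.2, #18).** "ICU status (among those not in an ICU at baseline, record if transferred to the ICU or the need to transfer to the ICU". The need part carries a condition: "the need to transfer to the ICU [if the ICU is not available". The protocol has the same definition in the Synopsis (1.1) and in Section 3, Table 2.
- **Analysis (SAP 2.4.4.2).** The outcome becomes "18: % of patients with ICU use (among those not in an ICU at baseline". It is analysed by a stratified CMH test, with a difference, a 95% interval and a p-value for each dose.
- **Objective (SAP 1.2.2).** "Evaluate need for admission into intensive care unit (ICU".
- **Eligibility (Protocol 5.1, I 02).** One of three alternative routes to critical disease is "Requiring treatment in an intensive care unit". It is worded as need, not location.
- **Baseline data (SAP 2.1.1).** "ICU required (Yes, No") and then "If yes, ICU admitted (Yes, No"). A patient who needs an ICU but has not been admitted to one is thus a baseline state that the plan foresees.

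**The concern.** The rule for entering the denominator and the rule for counting an event use different concepts. A patient leaves the denominator only by being in an ICU at baseline, but can become an event through need. A patient with ICU required = Yes and ICU admitted = No at baseline stays in, with a need that study drug cannot have prevented.

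If such patients are counted, #18 mixes new deterioration after treatment with a condition present at entry, and the treatment effect on new ICU need is diluted.

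A second, separate mismatch lies between the definition (transfer, or need if no ICU is available) and the analysis label (ICU use). Two programmers working from the two sections could derive different event counts.

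**Working it through.** **1. What happens to each type of patient under the definition in SAP 2.1.3.2**

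| ICU required at baseline | ICU admitted at baseline | In denominator? | Can need from before dosing produce an event? |
|---|---|---|---|
| No | not asked | Yes | No |
| Yes | Yes | No | Not applicable |
| Yes | No, no ICU available | Yes | Yes, at entry |
| Yes | No, ICU available | Yes | Yes, on later transfer; no event if the need resolves first |

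The last two rows are the affected group. No text for #18 in SAP 2.4.4.2, and no convention in SAP 2.5.2, requires the need to be new or to arise after the first dose.

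**2. Comparison within the same list.** Endpoint #16 (start of ventilation or high-flow support) is limited to patients who did not require those supports at baseline. It excludes on requirement; #18 excludes on location only.

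**3. Size.** The plan states no rate, count or power for #18, so there is no figure to reproduce. Let f be the affected share of the denominator, p the true rate of new events in the other patients, and q the event probability in affected patients.

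- Observed rate in an arm = f·q + (1 − f)·p.
- If q is the same in both arms, the difference is (1 − f)·(p_placebo − p_sarilumab), so the risk difference falls by the fraction f whatever q is. If treatment also lowers q, it falls by less.
- The risk ratio is diluted most at q = 1 and not at all at q = 0.

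Neither f nor p is in the documents. Both are assumed below, with q = 1 as the upper bound.

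| f | True 20% vs 12% | Difference | RR | True 30% vs 20% | Difference | RR |
|---|---|---|---|---|---|---|
| 0 | 20.0% vs 12.0% | 8.0 | 0.60 | 30.0% vs 20.0% | 10.0 | 0.67 |
| 5% | 24.0% vs 16.4% | 7.6 | 0.68 | 33.5% vs 24.0% | 9.5 | 0.72 |
| 10% | 28.0% vs 20.8% | 7.2 | 0.74 | 37.0% vs 28.0% | 9.0 | 0.76 |
| 20% | 36.0% vs 29.6% | 6.4 | 0.82 | 44.0% vs 36.0% | 8.0 | 0.82 |

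Example: 0.10 + 0.90 × 0.20 = 0.280 and 0.10 + 0.90 × 0.12 = 0.208; 0.208 / 0.280 = 0.74.

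**4. Does the smaller denominator cancel the gain?** Take assumed true rates of 30% versus 15% and an assumed 60 placebo and 120 sarilumab patients. Use an unstratified two-sided 5% comparison of proportions: power = Φ((difference − 1.96·SE0)/SE1), with SE0 from the pooled rate and SE1 from the separate rates.

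| f | Power as written (60 vs 120, q = 1) | Power after excluding affected patients |
|---|---|---|
| 0 | 65% | 65% (60 vs 120) |
| 5% | 56% | 63% (57 vs 114) |
| 10% | 48% | 61% (54 vs 108) |
| 20% | 35% | 56% (48 vs 96) |

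Example at f = 10% after exclusion: the pooled rate is 0.20, SE0 = √(0.16 × (1/54 + 1/108)) = 0.0667, SE1 = √(0.21/54 + 0.1275/108) = 0.0712, and (0.150 − 1.96 × 0.0667)/0.0712 = 0.27, which gives 61%. In this upper-bound illustration, exclusion costs less than dilution.

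**The case against.** A reader might infer that everyone enrolled because of ICU need is an event at entry. The documents do not support that. Patients already in an ICU are excluded. The need part applies only if no ICU is available, so among the rest only those with no available ICU could be events at entry. The others count on later transfer, or not at all.

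A reader might also infer that the SAP deliberately counts need from before dosing. It does not say so. It is silent, and the definition can be read as describing something observed during follow-up. That is a fair reading, but the text does not secure it, and the denominator still keeps these patients either way.

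The two mismatches also should not be added together as if both harms must occur. An event at entry needs the transfer-or-need definition. Dependence on bed supply needs ICU use to mean actual admission, and under that reading only the delayed-transfer route remains. ICU use may simply be a short label, since SAP 2.4.4.2 refers back to the endpoints in 2.1.3.2.

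Finally, the stakes are limited, and this stands in full. The affected group may be small, and E 01 (unlikely to stay at the site beyond 48 hours) may remove some patients awaiting a bed elsewhere. Randomization and the CMH test are stratified by severity, so correctly stratified affected patients fall in the critical strata and are balanced in expectation. No multiplicity-controlled claim depends on #18 (SAP 2.4.4.3).

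**Conclusion.** The point holds as a mismatch between denominator and event. Patients who require an ICU but are not in one at baseline remain in #18 and can count as events for need present before dosing. The risk difference is diluted toward zero by up to the affected share. That share is unknown from the documents, and the 5% to 20% range and all event rates above are assumptions. The risk ratios and the as-written power figures are upper bounds on the dilution at each share, because they treat every affected patient as a certain event. No systematic bias between arms is expected, and neither the primary nor the key secondary conclusion is touched.

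Separately, the label in SAP 2.4.4.2 does not match the event in SAP 2.1.3.2 or the objective in SAP 1.2.2. That should be reconciled even if no patient turns out to be in the affected group.

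**What to change.** 1. In SAP 2.1.3.2 and 2.4.4.2, restrict #18 to patients with ICU required = No at baseline, in line with #16, and count only events after the first dose.
2. In SAP 2.4.4.2, replace ICU use with the event from 2.1.3.2: transfer, or need for transfer if no ICU is available.
3. Put the same at-risk wording in the protocol endpoint lists (Synopsis 1.1 and Section 3, Table 2).
4. Confirm that need after baseline is captured on the CRF. SAP 2.1.1 lists ICU required only at baseline, and the daily data named in Protocol 1.3 (footnote 11) and 8.1.1 are ICU admission and discharge. If need is not captured, keep the baseline restriction, use transfer as the event, and state that the result then depends on ICU availability.

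The baseline restriction uses items already planned for collection, and their summary will also show how large the affected group is. The costs are a slightly smaller denominator, a short edit to both documents, and the CRF check. The change should be settled before the primary database lock.
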